7.1.2.2. IPTW with stabilized weights[6]

IPTW with stabilized weights will be used to balance patient characteristics between two groups using propensity score calculated by using a multivariable logistic model as mentioned above (see above 7.1.2.1). However, if a treated patient has a very low propensity score, a very large weight can be created. Large weights can increase the variability of estimated treatment effect. In order to address this, the weights can be stabilized. Stabilized weights will be calculated by using a formula shown below, by multiplying the treatment and control weights by a constant, equal to the expected value of being in the treatment or comparison cohorts, respectively.

 $W_i = \frac{Z}{PS_i} + \frac{1-Z}{1-PS_i}$, z: probability of treatment without considering covariates PFIZER CONFIDENTIAL

The distribution of the stabilized weight will be reviewed. If there are extreme outliers, the large weights could be set to a less extreme value (e.g. recoding all weights that are outside 5th and 95th percentile). If needed, truncation can be done after stabilizing the weights. After the weights are applied, the balance of the baseline covariates will be assessed. First, the means and proportions of baseline variables are compared. The standardized difference compares the difference in means in units of the standard deviation. If the standardized difference is less than 10%, the covariates are considered balanced.

7.1.2.3. Calculation of event rate

Patients who experience a clinical endpoint event after the earlier of their discontinuation of the index OAC, switching from the index OAC, withdrawal from the database, or the end of intended follow-up period will be censored. Patients who do not experience a clinical endpoint event will be censored at the earlier of their discontinuation of the index OAC, switching from the index OAC or withdrawal from the database will be censored.

Using the number of patients who experience each endpoints and the total observation period, incidence rate of each endpoint will be calculated and be presented as per 1,000 person-years.

7.1.2.4. Kaplan-Meier Method

For each endpoint, Kaplan-Meier curves will be plotted for the time from the index date to first event by index OAC treatment in each of the IPTW cohorts. The log-rank test is used for comparison between two curves.

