2.1. STUDY DESIGN

This is a retrospective non-intervention observational study to evaluate the difference in safety and effectiveness between apixaban and warfarin using a database provided by Medical Data Vision Co. Ltd. (MDV Co. Ltd.). Eligible patients will be extracted from the database and allocated to the pre-defined cohorts based on the actual age, age of NVAF diagnosis and types of anticoagulant therapy.

Based on the age category and anticoagulants on the index date (a date when patients initiated an anticoagulant for prevention of stroke/SE), eligible patients will be allocated to some cohorts. Patient characteristics will be balanced by an Inverse probability of treatment weighting (IPTW) method, and risk of stroke/SE (primary effectiveness endpoint) and major bleeding (primary safety endpoint) will be compared. Hazard ratios and 95% confident intervals will be calculated by using a Cox proportional hazard method with a robust sandwich variance estimator to account for induced correlations among weighted patients.

PFIZER CONFIDENTIAL

Page 5 of 51

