5. ENDPOINTS AND COVARIATES

5.1. EFFICACY/EFFECTIVENESS ENDPOINT(S)

5.1.1. Primary effectiveness endpoint and primary analyses

Primary effectiveness endpoint is incidence of a composite of Stroke/SE ("cardiogenic cerebral embolism", "cerebral infarction", hemorrhargic stroke or SE) in NVAF patients treated with warfarin or apixaban. TIA is not included in the outcome (not regarded as stroke).

- 1. Incidence of stroke/SE (per 1,000 person-year)
- Survival curves of stroke/SE-free patients (Kaplan-Meier curves) will be drawn for apixaban and warfarin cohorts. Difference in the two curves will be evaluated by a Logrank test.

Risk of stroke/SE in each cohort will be compared between balanced warfarin and balanced apixaban cohorts by using Cox proportional hazard analysis. Hazard ratio with 95% confident intervals will be calculated.

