7.1.2. Patient characteristics balancing

In this study, cohorts with balanced patient characteristics (s-IPTW warfarin cohort and s-IPTW apixaban cohort) will be created from raw cohorts (raw warfarin and raw apixaban cohorts). A propensity score will be calculated based on multivariable logistic regressions in order to account for confounding effects and to ensure that patient characteristics will be balanced between the warfarin cohort and apixaban cohort. An inverse probability of treatment weighting (IPTW) method using the calculated propensity score will be applied. To avoid sample size inflation and to ensure appropriate estimation of variances, s-IPTW (stabilized IPTW) will be used here.

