7.1.2.5. Calculation of hazard ratio with 95% confident intervals

Cox proportional hazards model will be used to compare endpoints in each of the sIPTW cohorts, with robust sandwich estimates to account for the clustering within balanced sets. The Cox proportional hazards model will include only index OAC treatment (apixaban or warfarin) as the independent variable if patient characteristics are well balanced between groups based on standardized difference in components of the PS. If not balanced, the unbalanced variable will be also included to the model in addition to the index OAC treatment. The hazard ratios with corresponding 95% confidence intervals and p-values will be reported.

PFIZER CONFIDENTIAL

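### The log-rank test on the weighted Kaplan-Meier curves has no stated weighting or robust variance; with the standard variance its p-value is too small once the weights vary appreciably

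*SAP*

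**What the plan says.** SAP 7.1.2.4 states that "Kaplan-Meier curves will be plotted for the time from the index date to first event by index OAC treatment in each of the IPTW cohorts", for every endpoint, and then that "The log-rank test is used for comparison between two curves". SAP 5.1.1 (stroke/SE) says "Difference in the two curves will be evaluated by a Logrank test", and 5.2.1 says the same for major bleeding. Both sections cover the primary analyses of their endpoint. None of the three says how the weights enter the test or how its variance is estimated, and Appendix 2, for additional statistical methodology, is marked not applicable.

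For the Cox model the SAP is explicit. Section 2.1 specifies a "robust sandwich variance estimator to account for induced correlations among weighted patients", and 7.1.2.5 fits the model "with robust sandwich estimates to account for the clustering within balanced sets". Section 7.1.2.5 adds that "The hazard ratios with corresponding 95% confidence intervals and p-values will be reported".

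On the weights, 7.1.2 says "To avoid sample size inflation and to ensure appropriate estimation of variances, s-IPTW (stabilized IPTW) will be used here". Section 7.1.2.2 plans a review of the weight distribution and optional truncation, for example "recoding all weights that are outside 5th and 95th percentile". Section 3.1 states no hypotheses. Section 3.2 refers statistical evaluations to an alpha of 0.05 without saying which p-value decides.

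**The concern.** The same weighted data feed two tests for each primary endpoint. One has a variance suited to weighting and the other has none stated. A log-rank routine that takes the weights as counts treats a patient with weight 2 as two independent patients, so it understates the variance whenever the weights vary. Stabilising brings the average weight to about 1, so the total sample size is not inflated, but it does not remove the spread that causes this problem.

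Each primary endpoint would then be reported with two p-values read against 0.05, and the log-rank value would tend to be the smaller. The SAP does not say which one governs. Because 7.1.2.4 covers each endpoint, the secondary bleeding and stroke outcomes are affected too. No power is shown for those, so borderline results are more likely there.

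**Working it through.** **1. The plan's own figures.** SAP Table 2 uses type I error 0.05, type II error 0.2, a 1:1 ratio, hazard ratios of 0.59 (major bleeding) and 0.53 (stroke/SE), and annual rates of 2.5% and 1.18%, and of 1.92% and 0.98%. Schoenfeld's formula with two-sided alpha is events = 4(1.960 + 0.842)² / (ln HR)².
- Major bleeding: 112.8, rounded up to 113. 113 / 0.0184 = 6,141 patients.
- Stroke/SE: 77.9, rounded up to 78. 78 / 0.0145 = 5,379 patients.

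Both match Table 2. The sample size is not in dispute. It supplies a realistic size and event rate for step 3.

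**2. Variance of the weighted log-rank.** The weighted log-rank score sums w(a − p) over events, where a is the treatment indicator and p the weighted share of the risk set on apixaban. With weights as counts, its variance is the sum of w·p(1 − p). For rare events the true variance is close to the sum of w²·p(1 − p). The ratio of true to standard variance is therefore about E[w²]/E[w], which is 1 + CV² when the mean weight is 1. Hence

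actual alpha ≈ 2[1 − Φ(1.960 / √(1 + CV²))].

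The standard test is significant while the robust one is not when the standard z lies between 1.960 and 1.960·√(1 + CV²). The last column gives that band as standard p-values.

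| Weight CV (assumed) | 1 + CV² | Actual alpha | Standard p-values that would not survive a robust variance |
|---|---|---|---|
| 0.25 | 1.0625 | 5.7% | 0.043 to 0.05 |
| 0.50 | 1.25 | 8.0% | 0.028 to 0.05 |
| 0.75 | 1.5625 | 11.7% | 0.014 to 0.05 |

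**3. Simulation under no treatment effect.** Set-up: 6,141 patients, mean event rate 1.84% per year, a logistic propensity score on five covariates, conventional stabilised weights and 2,000 runs per setting (Monte Carlo standard error about 0.5 points). The two values in each cell are for covariates without and with an effect on the outcome.

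| Weights | Mean CV | Weighted log-rank, standard variance | Weighted log-rank, robust variance |
|---|---|---|---|
| Untruncated | 0.26 | 6.0%, 4.8% | 5.5%, 4.2% |
| Untruncated | 0.44 | 6.7%, 7.3% | 4.5%, 4.4% |
| Untruncated | 0.65 | 10.2%, 11.8% | 4.6%, 5.7% |
| Same third setting, truncated at 5th/95th percentile | 0.42 | 5.7%, 12.2% | 4.7%, 10.2% |

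The untruncated rows agree with the formula: negligible inflation at CV near 0.25, clear inflation by 0.65, and a robust test at 4.2% to 5.7% throughout. Truncation narrows the gap between the two variances. The 10.2% in the last row reflects confounding left behind by truncation. That is a separate matter, which a robust variance does not cure.

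**4. What CV is plausible?** The documents give no weight distribution, so this is illustration only. Propensity scores are estimated by calendar year (7.1.2.1). If the numerator z in 7.1.2.2 is the overall apixaban share, and that share rose linearly over nine equal years, then CV² = mean of [z²/p + (1 − z)²/(1 − p)] − 1, where p is each year's share. A rise from 30% to 70% gives CV 0.28, from 20% to 80% gives 0.46, and from 10% to 90% gives 0.76. If z is taken within calendar year, this source disappears and only the 26 listed covariates contribute.

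**The case against.** **The text is silent, not wrong.** The SAP never says the test is unweighted or uses a standard variance. That is correct, and it is why the point concerns what is unspecified. It still matters, because the named test in its standard form is not valid on these data and the SAP specified a sandwich variance for only one of the two tests.

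**A reader might infer that the test will ignore the weights and compare the raw, confounded cohorts.** In the simulation such a test rejected a true null in 38% to 87% of runs with confounding. The documents do not support that reading. Section 7.1.2.4 compares curves drawn in the IPTW cohorts, and the summary in 7.2.4 gives the balanced cohorts as the analysis set for every Kaplan-Meier row. The size of those rates also depends on the confounding assumed. They form no part of this point.

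**The size depends on an undocumented CV, and truncation limits it.** Both parts stand. At a CV near 0.25 nobody would notice the difference.

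**The estimates are protected, and the log-rank is peripheral.** The Cox results use a robust variance. Section 2.1 describes the comparison only through Cox, and 7.2.4 does not list the log-rank. This confines the defect to one p-value but does not remove it, since 5.1.1 and 5.2.1 attach that p-value to the primary endpoints.

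**No conclusion would change at the planned size.** Table 1 lists 76,260 + 62,453 = 138,713 patients before eligibility. Assume 10% are eligible, with one year of follow-up each. That gives 13,871 × 0.0184 = 255 bleeding and 13,871 × 0.0145 = 201 stroke/SE events. With z = |ln HR|·√(events/4), z is 4.21 and 4.50. Dividing by 1.25 (CV 0.75) gives 3.37 and 3.60, so p is about 0.0007 and 0.0003. At 5% eligible, the p-values after the same division are about 0.017 and 0.011. If the SAP's hazard ratios hold, the two tests would therefore be expected to agree on the primary endpoints. Disagreement needs a weaker effect or a sparser endpoint.

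**Conclusion.** The point holds as an omission with a definite consequence. If the log-rank test is run with the weights and its standard variance, its type I error at nominal 5% is about 5.7%, 8.0% and 11.7% at weight CVs of 0.25, 0.5 and 0.75. These figures assume rare events, a mean weight of 1 and no truncation, and the CVs themselves are assumed.

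The defect is confined to the log-rank p-value. It would be wrong to infer that the study's hazard ratios, intervals or Cox p-values are invalid, or that the primary conclusions are in doubt. The practical risk is two conflicting p-values for one endpoint in a borderline result, with no rule for which to believe.

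**What to change.** - In SAP 7.1.2.4, 5.1.1 and 5.2.1, specify an s-IPTW-weighted log-rank test with robust (sandwich) variance as the p-value shown with the curves. This is equivalent to the robust score test from the s-IPTW Cox model with treatment as the only term. Alternatively, show the curves without a log-rank p-value.
- State that the robust Cox p-value in 7.1.2.5 governs inference for each endpoint.
- Section 7.1.2.5 adds any unbalanced covariate to the Cox model. If that happens, do not present the adjusted model's p-value as a test of the plotted curves, because it no longer tests them.

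The cost is a few sentences of SAP text. No new data are needed, and the robust score test comes from the treatment-only form of the model already planned.

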7.1.2.5. Calculation of hazard ratio with 95% confident intervals

Cox proportional hazards model will be used to compare endpoints in each of the sIPTW cohorts, with robust sandwich estimates to account for the clustering within balanced sets. The Cox proportional hazards model will include only index OAC treatment (apixaban or warfarin) as the independent variable if patient characteristics are well balanced between groups based on standardized difference in components of the PS. If not balanced, the unbalanced variable will be also included to the model in addition to the index OAC treatment. The hazard ratios with corresponding 95% confidence intervals and p-values will be reported.

PFIZER CONFIDENTIAL

7.2. STATISTICAL ANALYSIS

7.2.1. Safety Analysis

This is a database study and safety analyses will not be performed because it is not possible to identify adverse events directly caused by the drug or suspected to be related to the drug. Only incidence of major bleeding, occurred during the follow-up periods, will be compared between s-IPTW apixaban and warfarin cohorts. See 5.2.1 and 7.1 above.

7.2.2. Analysis of Efficacy Analysis

See 7.1 above

7.2.3. Sensitivity analysis

E-values will be calculated to assess the extent of unmeasured confounding on findings from primary analyses of effectiveness and safety outcomes. E-value is a measure developed by VanderWeele and Ding (2017) as the minimal strength of association between a hypothetical unmeasured confounder with both the treatment and outcome to explain away the identified association between treatment and the outcome.

PFIZER CONFIDENTIAL

Page 19 of 51

7.2.4. Summary of Analyses

Outcome	Analysis Set	Endpoint	Subgroup	Statistical Method	Covariates/Strata	Missing Data
Incidence rate of stroke/SE	Balanced cohorts	Primary effectiveness	None	1000 person-years	Refer to 5.1.1	No imputation
Incidence of cardiogenic cerebral embolism	Balanced cohorts	Secondary effectiveness	None	1000 person-years	Refer to 5.1.2	No imputation
Incidence of cerebral infarction	Balanced cohorts	Secondary effectiveness	None	1000 person-years	Refer to 5.1.2	No imputation
Incidence rate of major bleeding	Balanced cohorts	Primary safety	None	1000 person-years	Refer to 5.2.1	No imputation
Incidence rate of intracranial hemorrhage	Balanced cohorts	Secondary safety	None	1000 person-years	Refer to 5.2.2	No imputation
Incidence rate of gastrointestinal bleeding	Balanced cohorts	Secondary safety	None	1000 person-years	Refer to 5.2.2	No imputation
Incidence of rate of intraocular bleeding	Balanced cohorts	Secondary safety	None	1000 person-years	Refer to 5.2.2	No imputation
Time course of proportion of stroke/SE -free NVAF patients	Balanced cohorts	Primary effectiveness	None	Kaplan-Meier curves	Refer to 5.1.1	No imputation
Time course of proportion of cardiogenic cerebral embolism-free NVAF patients	Balanced cohorts	Secondary effectiveness	None	Kaplan-Meier curves	Refer to 5.1.2	No imputation
Time course of proportion of cerebral infarction"-free NVAF patients	Balanced cohorts	Secondary effectiveness	None	Kaplan-Meier curves	Refer to 5.1.2	No imputation

PFIZER CONFIDENTIAL

Page 20 of 51

Time course of proportion of major bleeding- free NVAF patients	Balanced cohorts	Primary safety	None	Kaplan-Meier curves	Refer to 5.2.1	No imputation
Time course of proportion of intracranial hemorrhage-free NVAF patients	Balanced cohorts	Secondary safety	None	Kaplan-Meier curves	Refer to section 5.2.2	No imputation
Time course of proportion of gastrointestinal bleeding-free NVAF patients	Balanced cohorts	Secondary safety	None	Kaplan-Meier curves	Refer to section 5.2.2	No imputation
Time course of proportion of intraocular bleeding-free NVAF patients	Balanced cohorts	Secondary safety	None	Kaplan-Meier curves	Refer to section 5.2.2	No imputation
Risk of stroke/SE during the follow-up period in NVAF patients (Hazard ratio, apixaban versus warfarin)	Balanced cohorts	Primary endpoint	None	Cox proportional hazards regression model	Refer to 5.1.1	No imputation
Risk of cardioembolic stroke during the follow-up period in NVAF patients (Hazard ratio, apixaban versus warfarin)	Balanced cohorts	Secondary effectiveness	None	Cox proportional hazards regression model	Refer to 5.1.2	No imputation
Risk of cerebral infarction during the follow- up period in NVAF patients (Hazard ratio, apixaban versus warfarin)	Balanced cohorts	Secondary effectiveness	None	Cox proportional hazards regression model	Refer to 5.1.2	No imputation
Risk of major bleeding during the follow-up period in NVAF patients (Hazard ratio, apixaban versus warfarin)	Balanced cohorts	Primary safety	None	Cox proportional hazards regression model	Refer to 5.2.1	No imputation
Risk of intracranial hemorrhage during the follow-up period in NVAF patients (Hazard ratio, apixaban versus warfarin)	Balanced cohorts	Secondary safety	None	Cox proportional hazards regression model	Refer to 5.2.2	No imputation
Risk of gastrointestinal tract bleeding during the follow-up period in NVAF patients (Hazard ratio, apixaban versus warfarin)	Balanced cohorts	Secondary safety	None	Cox proportional hazards regression model	Refer to 5.2.2	No imputation

Page 21 of 51

Risk of intraocular bleeding during the follow-up period in NVAF patients (Hazard ratio, apixaban versus warfarin)	Balanced cohorts	Secondary safety	None	Cox proportional hazards regression model	Refer to 5.2.2	No imputation
--	------------------	---------------------	------	---	----------------	---------------

Page 22 of 51

8. LIST OF TABLES AND TABLE SHELLS

None

10. APPENDICES

10.1. APPENDIX 1: DATA DERIVATION DETAILS

Not applicable

10.2. APPENDIX 2: ADDITIONAL STATISTICAL METHODOLOGY DETAILS

Not applicable

10.3. APPENDIX 3: DIAGNOSIS AND PROCEDURE CODES USED IN THE STUDY

10.3.1. List of diagnosis code

Variable Used in Study	ICD-10 Code [*]	Additional rules on Data Extraction
Atrial fibrillation	148	
Post-operative atrial fibrillation	8847772	Standard disease code
Valvular atrial fibrillation	8846941	Standard disease code

PFIZER CONFIDENTIAL

Variable Used in Study	ICD-10 Code [*]	Additional rules on Data Extraction
Rheumatic atrial fibrillation	105	
	106	
	107	
	108	
	109	
Mechanical-valvular atrial fibrillation	T820	
Hyperthyroidism or thyrotoxicosis	E05	
Heart failure	1110	
	1500	
	1501	Exclude cardiac asthma
	1509	
Hypertension	H208	Include only hypertensive iridocyclitis
	H350	Include only hypertensive retinopathy and hypertensive neuroretinopathy
	110	
	l110	
	I119	
	l120	
	1129	Include only hypertensive renal disease, hypertensive nephropathy and hypertensive nephrosclerosis
	1139	
	1150	
	1151	
	1152	
	1158	
	1159	
	l619	Include only hypertensive intracerebral hemorrhage
	1674	
Diabetes	E10	
	E11	
	E12	
	E13	
	E14	
Hemorrhage stroke	160	
	l61	
	162	Exclude non-traumatic extradural haemorrhage

Page 24 of 51

Variable Used	ICD-10	Additional rules
in Study	Code*	on Data Extraction
Ischemic stroke	163	
	3489032	standard disease code
	4371003	
	4379014	
	3448002	
	3448028	
	3489029	
	3489035	
	4379006	
TIA	H340	
	G450	
	G451	
	G458	
	G459	
Systemic embolism	1740	Include only abdominal aortic embolism
	1741	Include only aortic embolism
	1742	Include only acute arterial occlusive disease of arteries of upper extremities
	1743	Include only femoral arterial occlusion and acute arterial occlusive disease of arteries of lower extremities
	1744	
	1745	Include only iliac artery embolism
	1748	Include only hepatic artery embolism
	1749	Include only thromboembolism, embolic infarction, aortic embolism
Peripheral vascular disorder	1702	Include only atherosclerosis and arteriosclerosis obliterans
	1709	
	1731	Include only Buerger's disease
	1739	Exclude peripheral circulatory failure, cerebrovascular spasm, and angiospasm pf the extremities
	1742	
	1743	
	1745	
	1748	Include only subclavian artery stenosis
Aortic plaque	4400011	Standard disease code
	8837393	Standard disease code
Coronary artery disease	1200	

Page 25 of 51

Variable Used	ICD-10	Additional rules
in Study	Code [*]	on Data Extraction
	1208	
	1209	
	1200	
	1210	
	1212	
	1212	
	1214	
	1240	
	1210	
	1248	
	1210	
	1252	Exclude calcification of coronary artery
	1252	
	1258	Exclude coronary arteritis
	1259	
Myocardial infarction	1200	Exclude intermediate angina syndrome, preinfarction
	1200	syndrome, initial arbeits angina, intermediate coronary syndrome
	1210	
	l211	
	1212	
	1214	
	1240	
	1241	Exclude Dressler syndrome
Renal impairment	1120	
	1129	
	1139	
	N003	
	N009	
	N032	
	N033	
	N039	
	N040	
	N044	
	N049	
	N052	

Page 26 of 51

Variable Used	ICD-10	Additional rules
in Study	Code [*] N055	on Data Extraction
	N055	
	N059	
	N170	
	N171	
	N172	
	N178	
	N179	
	N189	
	N19	Exclude renal anemia, afunctional kidney, and alimentary proteinuria
Liver dysfunction	B150	
	B159	
	B162	
	B169	
	B171	
	B172	
	B178	
	B179	
	B181	
	B182	
	B189	
	B190	
	B199	
	C220	
	K700	
	K701	
	K703	
	K709	
	K716	
	K720	
	K721	
	K729	
	K730	
	K732	
	K738	
	K739	
	K740	

Page 27 of 51

Variable Used in Study	ICD-10 Code [*]	Additional rules on Data Extraction
	K741	
	K743	
	K744	
	K745	
	K746	
	K750	
	K751	
	K754	
	K759	
	K760	
	K761	
	K762	
	K763	
	K766	
	K767	
	K768	
	K769	
Cancer	C00	
	C01	
	C02	
	C03	
	C04	
	C05	
	C06	
	C07	
	C08	
	C09	
	C10	
	C11	
	C12	
	C13	
	C14	
	C15	
	C16	
	C17	
	C18	
	C19	

Page 28 of 51

Variable Used in Study	ICD-10 Code [*]	Additional rules on Data Extraction
	C20	
	C21	
	C22	
	C23	
	C24	
	C25	
	C26	
	C30	
	C31	
	C32	
	C33	
	C34	
	C37	
	C38	
	C40	
	C41	
	C43	
	C44	
	C45	
	C46	
	C47	
	C48	
	C49	
	C50	
	C51	
	C52	
	C53	
	C54	
	C55	
	C56	
	C57	
	C58	
	C60	
	C61	
	C62	
	C63	

Page 29 of 51

Variable Used in Study	ICD-10 Code [*]	Additional rules on Data Extraction
	C64	
	C65	
	C66	
	C67	
	C68	
	C69	
	C70	
	C71	
	C72	
	C73	
	C74	
	C75	
	C76	
	C78	
	C79	
	C80	
	C81	
	C82	
	C83	
	C84	
	C85	
	C88	
	C90	
	C91	
	C92	
	C93	
	C94	
	C95	
	C96	
	C97	
	D00	
	D01	
	D02	
	D03	
	D04	
	D05	

Page 30 of 51

Variable Used in Study	ICD-10 Code [*]	Additional rules on Data Extraction
	D06	
	D07	
	D09	
	D10	
	D11	
	D12	
	D13	
	D14	
	D15	
	D16	
	D17	
	D18	
	D19	
	D20	
	D21	
	D22	
	D23	
	D24	
	D25	
	D27	
	D28	
	D29	
	D30	
	D31	
	D32	
	D33	
	D34	
	D35	
	D36	
	D37	
	D38	
	D39	
	D40	
	D41	
	D42	
	D43	

Page 31 of 51

Variable Used in Study	ICD-10 Code [*]	Additional rules on Data Extraction
	D44	
	D45	
	D46	
	D48	

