5.2. SAFETY ENDPOINTS

5.2.1. Primary safety endpoint and primary analyses

Primary safety endpoint is incidence of major bleeding, which is defined as any bleeding requiring hospitalization.

1. Incidence of Major bleeding (per 1,000 person-year)

PFIZER CONFIDENTIAL

Page 11 of 51

- Survival curves of major bleeding-free patients (Kaplan-Meier curves) will be drawn for apixaban and warfarin cohorts. Difference in the two curves will be evaluated by a Logrank test.
- Risk of major bleeding in each cohort will be compared between balanced warfarin and balanced apixaban cohorts by using Cox proportional hazard analysis. Hazard ratio with 95% confident intervals will be calculated.

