7.1.2.1. Calculation of propensity score

Propensity scores will be estimated by calendar year of index date based on multivariable logistic regression analyses that incorporate potential predictors of therapy as independent variables in the regression and cohort status (prescription of warfarin or apixaban) as the outcome. Consecutive calendar years of index dates may be collapsed to build logistic regression model with robustness. The following covariates will be included in the logistic regression:

- age on index date
- age at NVAF diagnosis
- gender

PFIZER CONFIDENTIAL

- CHADS₂ score in baseline
- CHA₂DS₂-VASc score in baseline
- heart failure diagnosis in baseline
- coronary heart disease diagnosis in baseline
- peripheral arterial disorder diagnosis in baseline
- myocardial infarction diagnosis in baseline
- hyperthyroidism or thyrotoxicosis in baseline
- TIA diagnosis in baseline
- stroke or SE diagnosis in baseline
- renal dysfunction diagnosis in baseline
- liver dysfunction diagnosis in baseline
- bleeding diagnosis in baseline
- hypertension diagnosis in baseline
- diabetes mellitus diagnosis in baseline
- treated with antiplatelet drug in baseline
- treated with NSAIDs in baseline
- treated with gastric secretion inhibitor in baseline
- treated with statin-based drug in baseline
- treated with anti-hypertensives in baseline
- treated with anti-arrhythmics in baseline
- treated with beta-blockers in baseline
- treated with heparins in baseline
- cardioversion in baseline

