10.3.3. Stroke related medical history

Disease	ICD10 code	Standard disease code	Note
Homorrhago	160		
Hemorrhage stroke	l61		
SUDKE	162		Exclude non-traumatic extradural haemorrhage
	163		
		3489032	
		4371003	
		4379014	
Ischemic stroke		3448002	
		3448028	
		3489029	
		3489035	
		4379006	
	H340		
	G450		
TIA	G451		
	G458		
	G459		
	1740		Include only abdominal aortic embolism
	1741		Include only aortic embolism
	1742		Include only acute arterial occlusive disease of
	1/42		arteries of upper extremities
	1743		Include only femoral arterial occlusion and acute
Systemic			arterial occlusive disease of arteries of lower
embolism			extremities
	1744		
	1745		Include only iliac artery embolism
	1748		Include only hepatic artery embolism
	1749		Include only thromboembolism, embolic infarction, aortic embolism
	1748		Include only subclavian artery stenosis

10.3.4. bleeding

Procedure for definition of "bleeding"

Step 1. To extract the following group A or group B from MDV data base.

Group A: ICD-10 name includes "出血 (bleeding)" or "血腫 (ecchymoma)"

Group B: Disease name includes "出血 (bleeding)" or "血腫 (ecchymoma)"

Step 2. To select disease names considered to be relevant to side effect of OAC individually from disease names excluded in Step 1.

Step 3. To exclude disease names which are not considered to be relevant to side effect of OAC from the disease names included in Step 1.

ICD-10	ICD10Name
A162	Tuberculosis of lung, without mention of bacteriological or histological confirmation
A165	Tuberculous pleurisy, without mention of bacteriological or histological confirmation

ICD-10	ICD10Name				
B303	Acute epidemic haemorrhagic conjunctivitis (enteroviral)				
D500	Iron deficiency anaemia secondary to blood loss (chronic)				
D62	Acute posthaemorrhagic anaemia				
D66	Hereditary factor VIII deficiency				
D683	Haemorrhagic disorder due to circulating anticoagulants				
D698	Other specified haemorrhagic conditions				
D699	Haemorrhagic condition, unspecified				
E078	Other specified disorders of thyroid				
E274	Other and unspecified adrenocortical insufficiency				
G361	Acute and subacute haemorrhagic leukoencephalitis [Hurst]				
G951	Vascular myelopathies				
G968	Other specified disorders of central nervous system				
H052	Exophthalmic conditions				
H113	Conjunctival haemorrhage				
H168	Other keratitis				
H208	Other iridocyclitis				
H210	Hyphaema				
H313	Choroidal haemorrhage and rupture				

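### The systemic embolism code list admits femoral arterial occlusion (I743) without an acute or embolic limit, so a non-acute occlusion can count as a primary stroke/SE event; a subclavian stenosis row in SAP 10.3.3 also conflicts with 10.3.1

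*SAP*

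**What the plan says.** SAP 5.1.1: "Primary effectiveness endpoint is incidence of a composite of Stroke/SE", with SE as one component. It excludes TIA but states no condition on acuteness, admission, treatment or new onset. SAP 5.2.1 does set such a condition for the safety endpoint: "Primary safety endpoint is incidence of major bleeding, which is defined as any bleeding requiring hospitalization".

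SAP 10.3.1, systemic embolism rows:
- I743: "Include only femoral arterial occlusion and acute arterial occlusive disease of arteries of lower extremities".
- I742: "Include only acute arterial occlusive disease of arteries of upper extremities".
- I745: "Include only iliac artery embolism".
- I748: "Include only hepatic artery embolism".
- I740 and I741 are each limited to a named embolism, and I749 to thromboembolic or embolic names. I744 carries no note.

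The peripheral vascular disorder block of the same table lists I742, I743 and I745 with no note, and I748 limited to subclavian artery stenosis.

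SAP 10.3.3 repeats the systemic embolism rows for stroke-related history and then prints a second I748 row: "Include only subclavian artery stenosis".

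SAP 7.1.2.1 enters a history of stroke or SE, and "peripheral arterial disorder diagnosis in baseline", in the propensity score. Neither is an exclusion in SAP 4.1.2.

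**The concern.** The I743 row names two diseases, and the acute qualifier belongs only to the lower-extremity one. Its upper-limb counterpart, I742, is limited to acute disease. Because I743 also appears without restriction as peripheral vascular disorder, every I743 record that counts as SE also falls inside the SAP's own definition of background vascular disease.

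Nothing downstream screens such a record out. SAP 5.1.1 has no further condition, and no rule states how a code already present at baseline is treated when it reappears after index. Appendices 1 and 2, where such a rule could sit, are marked not applicable. Under Protocol 9.1 the first composite event ends follow-up for that outcome, so a femoral record would also stop the patient contributing a later stroke.

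At stake is the meaning of the primary effectiveness estimate. Non-embolic occlusions raise the reported stroke/SE rates and, if equally frequent in both arms, pull the hazard ratio toward 1. The subclavian row is a separate inconsistency: a stenosis is not an embolism, and two tables of the same SAP classify it differently.

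**Working it through.** **1. The code rows side by side (SAP 10.3.1)**

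| Code | Limit under systemic embolism | Under peripheral vascular disorder |
|---|---|---|
| I740, I741 | embolism | not listed |
| I742 | acute disease | listed, no limit |
| I743 | femoral term: none; other term: acute | listed, no limit |
| I744 | no note | not listed |
| I745 | embolism | listed, no limit |
| I748 | hepatic artery embolism | subclavian artery stenosis |
| I749 | thromboembolic or embolic names | not listed |

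Three things follow.
- For I742 and I745 the SE rule still requires acute disease or embolism. Their presence in the vascular list lets no chronic disease into the endpoint.
- For I748 the SAP splits one code by disease name. This shows that a non-embolic name can sit under an I74 code, and that the authors could separate the two. For I743 no split is made.
- Among the codes shared by both lists, the femoral term in I743 is therefore the only route for non-acute disease into the endpoint.

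**2. The I748 row in 10.3.3.** It follows I749, out of numerical order, and its wording matches the last peripheral vascular row of 10.3.1. However, 10.3.3 contains no peripheral vascular block from which the row could have slipped, so as printed it belongs to systemic embolism.

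**3. The plan's own figures.** Inputs from SAP 4.5, Table 2: HR 0.53, alpha 0.05 (taken as two-sided), power 0.80, ratio 1:1, rates 1.92% and 0.98% per year.
- Events = 4(1.960 + 0.842)² / (ln 0.53)² = 31.395 / 0.4031 = 77.9, so 78.
- Patients = 78 / [(0.0192 + 0.0098)/2] = 78 / 0.0145 = 5,379.

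Both match Table 2 and are not in dispute.

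**4. Illustration of dilution.** Let c be the rate of non-embolic events per 1,000 person-years, assumed equal in both arms and added to a warfarin rate of 19.2 with a true HR of 0.53:

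observed HR = (0.53 × 19.2 + c) / (19.2 + c)

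- c = 0.5: 10.676 / 19.7 = 0.542.
- c = 1: 11.176 / 20.2 = 0.553.

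These values of c are 2.5% (0.5/19.7) and 5.0% (1/20.2) of warfarin-arm events. They are assumptions, because the documents give no frequency. The rate is the whole-cohort figure from the earlier study (CER3), while the HR is from its subgroup aged 80 or over.

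SAP 4.5 expects higher rates here, and that shrinks the shift. With an assumed warfarin rate of 30, c = 1 gives (15.9 + 1)/31 = 0.545.

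**5. Power.** At HR 0.553 the same formula gives 31.395 / 0.3504 = 89.6, so 90 events instead of 78. The feasibility counts are 76,260 apixaban and 62,453 warfarin patients before eligibility criteria, so power is not the issue.

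**The case against.** The strongest reply is that nothing in the SAP says femoral arterial occlusion is chronic. The authors chose the name deliberately under the systemic embolism heading, and they placed arteriosclerosis obliterans elsewhere, under I702. What the name captures depends on Japanese disease-name coding, which the documents do not show. This stands, and it limits the point to what the rule permits rather than what it will do.

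A reader might infer that the whole overlap between the two lists brings chronic disease into the endpoint. The table above shows that it does not: only the femoral term could.

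A reader might also see an error in one baseline record setting both the SE and the peripheral arterial terms of the propensity score (assuming the latter uses the peripheral vascular list). A covariate list may be broader than an outcome list, and the model already holds CHADS₂ and CHA₂DS₂-VASc beside their components. No loss of balance has been shown.

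The size is open to challenge too. The added rates have no source. If the earlier study used the same list, its 0.53 already contains such events and the illustration counts them twice; the documents do not settle this. The assumed bias also works against the superiority hypothesis.

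Finally, 10.3.3 is titled as medical history, so its stenosis row may affect only the baseline flag and not the outcome.

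None of this explains why the femoral term lacks the limit that its neighbours carry, or why the two tables disagree on I748.

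**Conclusion.** The point holds in a narrow form. As written, the I743 row lets a non-acute femoral occlusion coded after index count as a primary stroke/SE event, and no other rule in the plan removes it. Separately, 10.3.3 and 10.3.1 disagree on subclavian artery stenosis.

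The frequency is unknown. Under the assumptions of equal rates in both arms, no effect of treatment on these events, and an earlier-study HR free of them, 0.5 to 1 added event per 1,000 person-years moves 0.53 to about 0.54–0.55. That is a modest shift toward 1; with unequal rates the direction would not be determined. The documents do not support saying that chronic disease makes up a material share of the endpoint, or that the study loses useful power. This is a correction to a primary-endpoint definition that should be made because it is specific and cheap.

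**What to change.** - In SAP 10.3.1, and in the matching row of 10.3.3, limit the I743 femoral term to acute or embolic disease names, consistent with I742.
- Keep the list as now printed as a sensitivity analysis, so that true femoral emboli and comparability with the earlier study are not lost.
- If the database has no acute or embolic femoral disease name, leave the term in and report the primary hazard ratio with and without it.
- Reconcile 10.3.3 with 10.3.1 by removing the subclavian stenosis row from systemic embolism, after checking it against the source file.
- Report SE events by code and arm, so that readers can see how much the femoral term contributes.

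The I742 and I745 entries under peripheral vascular disorder need not change.

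The cost is two code-list edits, a rerun of the flags on structured data already held, and one extra analysis. The main analysis may have slightly fewer SE events. Protocol 9.9 requires an amendment for major changes to a primary endpoint definition, so the sponsor should record whether this edit counts as one.
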